8.2. CLINICAL EVALUATION, LABORATORY TESTS AND FOLLOW-UP

Study procedures and timing are summarised in the Schedule for test and determinations (section 8.1).

- All immediate safety concerns must be discussed with the Sponsor immediately upon occurrence or awareness to determine if the participant should continue or discontinue treatment.
- Adherence to the study design requirements is essential and required for study conduct.
- All screening evaluations must be completed and reviewed to confirm that potential participants meet all eligibility criteria before inclusion. The investigator will maintain a patient log to record the details of all participants screened and to confirm eligibility or record reasons for screening failure, as applicable. Patient log will remain at the site at all time and will be available for monitoring and audit purposes.

8.2.1. Before treatment start

Informed Consent

For this study a single informed consent has been generated that includes the general information of the clinical trial and a section for the collection of samples for future research. The investigator or qualified designee must obtain documented consent from each potential subject or each subject's legally acceptable representative prior to participating in a clinical trial or Future Biomedical Research. The informed consent will adhere to EC requirements, applicable laws and regulations.

The following recommendations should be considered for informed consent procedure:

- Consent must be documented by the subject's dated signature or by the subject's legally acceptable representative dated signature on a consent form along with the dated signature of the person conducting the consent discussion.
- All fields aimed at collecting information of the patient and investigator performing the informed consent procedure should be completed. Any finding on signed consent forms could be considered as GCP breach.
- A copy of the signed and dated consent form should be given to the subject before participation in the trial. The initial informed consent form, any subsequent revised written informed consent form, and any written information provided to the subject must receive the EC approval or favourable opinion in advance of use.
- The subject or his/her legally acceptable representative should be informed in a timely manner if new information becomes available that may be relevant to the subject's willingness to continue participation in the trial. The communication of this information will be provided and documented through a revised consent form or addendum to the original consent form that captures the subject's dated signature or by the subject's legally acceptable representative dated signature.
- *Consent and Collection of Specimens for Future Biomedical Research:*
 - In accordance with Annex VIIIA - Guide for the elaboration of patient information sheet and informed consent of the AEMPS, taking into account that Future Biomedical Research will be offered to all patients, the information related to this part of the study will be included in a section of the general informed consent form. In this section, participation implications will be clearly explained, detailing the risk and benefit, answering all of patient's questions, and obtaining written informed consent before collection of biological samples.

- The patient may accept or NOT to participate in this optional collection of biological samples by marking the corresponding box YES/NO in the section of informed consent. Site staff obtaining the informed consent must verify that the patient has correctly completed all the sections including their willingness to participate or not in the collection of samples.
- The Principal Investigator or the designee should clearly indicate in patient records that the patient has signed the informed consent stating his willingness to participate in the GETNE T-1914 - CABATEN Study indicating the level of acceptance, clinical part +/- sample collection.

Medical History

- A medical history will be obtained by the investigator or qualified designee. Medical history will include all active conditions, any diagnosed condition that are considered to be clinically significant by the Investigator, and/or relevant medical history taking into consideration the eligibility criteria (section 6.1 and 6.2).
- Any autoimmune disorders, regardless of the onset date, should be recorded.

Physical Exam

- *Full Physical Exam:* The investigator or clinical designee will perform a full physical exam during the screening period. Clinically significant abnormal findings should be recorded as medical history.
- *Targeted Physical Exam (prior treatment administration):* Additional physical exams (targeted) should be performed based on investigator criteria as specified in the Trial Flow Chart-Section 8.1, considering the disease under study, patients' symptoms, and prior physical exams. After the first dose of trial treatment, new clinically significant abnormal findings should be recorded as AEs.

Vital Signs

- The investigator or qualified designee will take vital signs as specified in the Trial Flow Chart-Section 8.1.
- Vital signs should include temperature, pulse, respiratory rate, weight and blood pressure. Body weight is to be recorded at each visit along with vital signs, but height will be measured at screening only.

12-Lead Electrocardiogram (ECG)

A standard 12-lead ECG will be performed at baseline and at the end of the treatment visit using local standard procedure. Any clinically significant abnormalities detected require triplicate ECG results and should be recorded as medical history or adverse event, and monitored if needed. No new ECGs will be performed unless clinically indicated.

Prior and concomitant medications review

- *Prior Medications:*
The investigator or qualified designee will review prior medication use including any protocol-specified washout requirement, and record prior medication taken by the subject within 4 weeks of first dose of the study treatment.
- *Concomitant Medications:*
 - The investigator or qualified designee will record the medication, if any, taken by the subject during the trial from the time of signing the informed consent form until the Safety Follow-up Visit.
 - All medications related to reportable SAEs should be recorded
 -

Demography, Including Baseline Characteristics And Tobacco Use

- Date of birth (month/year of birth) or age at informed consent, race, and sex.
- Smoking history: never smoke (≤ 100 cigarettes/life time), former smoker (≥ 1 year), smoker, unknown)
- Tobacco use: pack/year and cigarettes/day.

Eligibility Criteria

All inclusion and exclusion criteria will be reviewed by the investigator or qualified designee to ensure that each subject qualifies for the trial. More details on criteria for patients' eligibility are in section 6.1 and 6.2.

Laboratory Assessments

The summary of the procedures required is summarised in Table 2 and flow chart (Section 8.1 and the corresponding footnotes). Laboratory tests for screening should be performed within 7 days prior to study enrolment. If performed < 14 days prior to the first dose of trial therapy, the screening laboratory tests will serve as cycle 1 day 1 laboratory tests. If not, laboratory tests will need to be performed again on day 1 of cycle 1. Laboratory determinations include full clinical chemistry panel (including albumin, alkaline phosphatase, LDH, calcium, magnesium, phosphorus, sodium, potassium, creatinine, creatine kinase, direct bilirubin, indirect bilirubin, total bilirubin, total protein, urea, uric acid, amylase, lipase, glucose, ALT, AST, ALP, GGT), hematological counts (total white blood cell count with leukocyte formula, haemoglobin, and platelet count), TSH hormone levels, serology (HIV, HBV, and HCV), urianalysis and tumor markers (NSE in tumors from cohort 1, CGA in tumors from cohort 5, cortisol in functionant tumors from cohort 3, metanephrides and, adrenaline in functionant tumors from cohort 4. Norepinephrine, 5-HIAA and CEA may be collected when considered).

Pregnancy test

A serum pregnancy test must be performed at screening (at the local laboratory) within ≤ 72 hours before the *first dose of study treatment (if clinically indicated)*.

Eastern Cooperative Oncology Group (ECOG) Performance Status

The investigator or qualified designee will assess ECOG performance status at screening, prior to the administration of each dose of trial treatment and as specified in the Table of Schedule of Assessments (Table 2). It is **important to collect ECOG Status in patient's record and eCRF**.

Biological samples collection

Tumour Biopsy (Archival, If Available)

- If available, it is mandatory that archival tumour tissue samples are analysed in this trial.
- Either pre-existing archived or newly-obtained (fresh tissue) biopsy specimens from either primary or metastatic tumour, whichever is the most recent.
- Tumour tissue specimen submitted in FFPE block is acceptable.

Processed blood samples:

- Serum and plasma samples to be collected at baseline, D1C2, and at progression.
- Blood samples are to be stored at site at -80°C , and are to be sent at the end of study (1 dry ice shipment per site).

Tumour Imaging

The site study team must review pre-trial images to confirm that the subject has at least one target lesion (i.e. meets measurability requirements) as per RECIST 1.1.

RECIST assessments will be performed on images from CT scans (preferred) or MRI, each preferably with IV contrast of the neck, chest, abdomen (including liver and adrenal glands), and pelvis. Pelvic imaging is recommended only when primary or metastatic disease in the pelvic region is likely. Patients with known baseline brain lesions are not eligible for this study, but brain CT scan or MRI is neither required at baseline nor in the follow-up in the absence of neurological signs or symptoms. Additional anatomical imaging should be carried out based on signs and symptoms of individual patients at baseline and follow-up. Baseline assessments should be performed no more than 28 days before the date of inclusion and, ideally, should be performed as close as possible to and prior to the start of treatment.

Quality of life (QoL)

The QoL measured by the self administered questionnaires EQ-5D-5L and EORTC QLQ-C30(appendix 2 and 3) will be performed at screening, no more than 28 days before the date of inclusion and, ideally, should be performed as close as possible to the start of treatment.

8.2.2. Assessment during treatment

Physical Exam

- *Targeted Physical Exam (prior treatment administration):* Additional physical exams (targeted) should be performed based on investigator criteria as specified in the Trial Flow Chart (Section 8.1), considering the disease under study, patient symptoms, and prior physical exams. After the first dose of trial treatment, new clinically significant abnormal findings should be recorded as AEs.

Vital Signs

- The investigator or qualified designee will take vital signs as specified in the Trial Flow Chart (Section 8.1).
- Vital signs should include temperature, pulse, respiratory rate, weight, and blood pressure. Body weight is to be recorded at each visit along with vital signs; however, height will be measured at screening only.

Laboratory Assessments

The summary of the procedures required is summarised in Section 8.1 and the corresponding footnotes. It is recommended that laboratory tests be performed < 3 days prior to the next dose of trial therapy in order to have the results to decide on the continuity of study treatment (dose modifications and delays, among other relevant clinical decisions).

Laboratory determinations include full clinical chemistry panel (including albumin, alkaline phosphatase, LDH, calcium, magnesium, phosphorus, sodium, potassium, creatinine, creatine kinase, direct bilirubin, indirect bilirubin, total bilirubin, total protein, urea, uric acid, amylase, lipase, glucose, ALT, AST, ALP, GGT), hematological counts (total white blood cell count with leukocyte formula, haemoglobin, and platelet count), TSH hormone levels, and tumor markers.

Tumor markers should be analyzed at screening and every 12 weeks \pm 2 weeks until PD or death (whichever occurs first) to determine the non-radiological response. The markers to collect are NSE in tumors from cohort 1, CGA in tumors from cohort 5, cortisol in functionant tumors from cohort 3, metanephhrines and, adrenaline in functionant tumors from cohort 4. Norepinephrine, 5-HIAA and CEA may be collected when considered.

Eastern Cooperative Oncology Group (ECOG) Performance Status

The investigator or qualified designee will assess ECOG performance status **prior to the administration** of each dose of atezolizumab as specified in the Table of Schedule of Assessments (Table 2). It is **important to**

collect ECOG Status in patient's record and eCRF.

Adverse Event (AE)/Serious Adverse Events (SAE) assessment

- The investigator or qualified designee will assess each subject to evaluate for potential new or worsening AEs as specified in the Trial Flow Chart, and subsequently if clinically indicated.
- Adverse events will be graded and recorded throughout the trial and during the follow-up period according to NCI CTCAE Version 5.0. Toxicities will be characterised in terms of seriousness, causality, toxicity grading, and action taken with regard to trial treatment.
- All AEs of unknown etiology associated with study treatment exposure should be evaluated to determine if it is possibly an ECI of a potentially immunologic etiology (termed immune-related adverse events, or irAEs).

Tumour Imaging

- q12w \pm 2w until the objective disease progression or death (whichever comes first). Image assessments by CT scan or MRI may be performed q8w \pm 2w if required by local standard clinical practice or by investigator criteria, as long as the frequency of assessments is maintained.

Biological samples collection

Processed blood samples:

- Serum and plasma samples to be collected at D1C2.
- Blood samples are to be stored at site at -80 °C and are to be sent at the end of study (1 dry ice shipment per site).

Pregnancy test

Women of childbearing potential are required to have a pregnancy test within 72 hours prior to the first dose of the study drug, and every 3 cycles (9 weeks) thereafter (if clinically indicated). Latest pregnancy results (maximum 9 weeks old) must be available and reviewed by the treating physician or investigator prior to commencing a new cycle of infusion. A urine or serum pregnancy test is acceptable.

Quality of life

The questionnaires EQ-5D-5L and EORTC QLQ-C30 will be fulfilled every two cycles by the patient during the visit, before the knowledge of tumor assessment and before the administration of each dose of atezolizumab as specified in the Table of Schedule of Assessments (Table 2).

8.2.3. End of treatment Visit

Physical Exam

- *Targeted Physical Exam (prior treatment administration):* Additional physical exams (targeted) should be performed based on investigator criteria as specified in the Trial Flow Chart-Section 8.1, considering the disease under study, patient symptoms, and prior physical exams. After the first dose of trial treatment, new clinically significant abnormal findings should be recorded as AEs.

Vital Signs

- The investigator or qualified designee will take vital signs as specified in the Trial Flow Chart-Section 8.1.

- Vital signs should include temperature, pulse, respiratory rate, weight, and blood pressure. Body weight is to be recorded at each visit along with vital signs; however, height will be measured at screening only.

12-Lead Electrocardiogram (ECG)

A standard 12-lead ECG will be performed at baseline and at end of treatment visit using local standard procedure. Any clinically significant abnormalities detected require triplicate ECG results and should be recorded as medical history or adverse event, and monitored if needed. No new ECGs will be performed unless clinically indicated.

Laboratory Assessments

The summary of the procedures required is summarised in Section 8.1 and in the corresponding footnotes. It is recommended that laboratory tests be performed < 3 days prior to the EOT visit.

Laboratory determinations include full clinical chemistry panel (including albumin, alkaline phosphatase, LDH, calcium, magnesium, phosphorus, sodium, potassium, creatinine, creatine kinase, direct bilirubin, indirect bilirubin, total bilirubin, total protein, urea, uric acid, amylase, lipase, glucose, ALT, AST, ALP, GGT), hematological counts (total white blood cell count with leukocyte formula, haemoglobin, and platelet count), TSH hormone levels, and tumor markers (NSE in tumors from cohort 1, CGA in tumors from cohort 5, cortisol in functionant tumors from cohort 3, metanephrides and, adrenaline in functionant tumors from cohort 4. Norepinephrine, 5-HIAA and CEA may be collected when considered).

Eastern Cooperative Oncology Group (ECOG) Performance Status

The investigator or qualified designee will assess ECOG performance status. It is **important to record ECOG Status in patient's record and eCRF**.

Adverse Event (AE)/Serious Adverse Events (SAE) assessment

- The investigator or qualified designee will assess each subject to evaluate for potential new or worsening AEs as specified in the Trial Flow Chart and more frequently if clinically indicated.
- Adverse events will be graded and recorded throughout the trial and during the follow-up period according to NCI CTCAE Version 5.0. Toxicities will be characterised in terms of seriousness, causality, toxicity grading, and action taken with regards to trial treatment.
- All AEs of unknown etiology associated with study treatment exposure should be evaluated to determine if it is possibly an ECI of a potentially immunologic etiology (termed immune-related adverse events, or irAEs).

Biological samples collection

Processed blood samples:

- Serum and plasma samples to be collected at progression.
- Blood samples are to be stored at site at -80 °C and are to be sent at the end of the study (1 dry ice shipment per site).

Quality of life

The QoL EQ-5D-5L, EORTC QLQ-C30 questionnaires (appendix 2 and 3) will be fulfilled by the patient during the EOT visit.

8.2.4. Post-treatment (Follow-up)

8.2.4.1. Progression Free Survival follow-up

After the end of the treatment visit, clinical procedures and assessment will be performed as previously explained and reflected in the summary table 2 (section 8.1), all patients will be followed by RECIST 1.1 every 12 weeks (+/-14 days) up to disease progression or death (whichever occurs first), independently of the reason for ending the treatment. Follow up assessments may be performed every 8 weeks (\pm 14 days) if required by local standard clinical practice or by investigator criteria, as long as the frequency of assessments is maintained. The follow-up period according to this protocol is 12 months considering last patient inclusion.

8.2.4.2. Overall Survival (Long term follow-up)

Follow-up after disease progression will be carried out according to local practice. The follow-up period according to this protocol is 12 months considering last patient inclusion. Information on subsequent treatments should include the list of post-treatment therapies, the drugs administered, the date of initiation/discontinuation of each drug and date of progression. All the data will be recorded in the medical record and in the eCRF.

Survival information may be obtained through telephone contact with the patient, patient's family or by contact with the patient's current physician. Survival data will be collected up to the time of the final overall survival (OS) analysis, and at this point, Investigators will be notified that no further data collection for the study is required.

The status of ongoing, withdrawn (from the study), and lost to follow-up patients at the time of an OS analysis should be obtained by the site personnel by checking the patient's notes and hospital records, contacting the patient's general clinician, and checking publicly available death registries.

9. ASSESSMENT OF SAFETY

Sites should record all adverse events both in patient's medical record and in eCRF according to the National Cancer Institute Common Terminology Criteria for Adverse Events (NCI-CTCAE) version 5.0, following the Table of assessment (Table 2, Section 8.1). For patients who are still on treatment at the end of trial, and for the additional 6 months with provision of both investigational products, any suspicion on adverse events/special situation should be reported to sponsor. Those events reported in patients receiving atezolizumab the marketing authorisation holder: Roche's Pharmacovigilance Department ([contact], [contact]). Those events reported in patients receiving cabozantinib the marketing authorisation holder: Ipsen's Pharmacovigilance Department ([contact], [contact]).

9.1. SAFETY PARAMETERS

Safety parameters are AE, SAE, AESI, pregnancy, medication error, overdose, drug abuse and drug misuse. Additional safety information could be derived from ECG, lab test, pregnancy test, or vital sign exam.

9.2. ADVERSE AND SERIOUS ADVERSE EVENTS

9.2.1. Definitions

Definitions regarding safety and pharmacovigilance to be applied in this study are defined below.

9.2.1.1. Adverse Event (AE)

An AE is any untoward medical occurrence in a patient or clinical investigation subject administered a medicinal product and that does not necessarily have a causal relationship with this treatment. An AE can therefore be the development of a new medical condition, or the deterioration of a pre-existing medical condition. This includes any unfavorable and unintended sign (e.g. tachycardia, enlarged liver), symptom (e.g. nausea, chest pain) or the abnormal results of an investigation (e.g. laboratory findings, electrocardiogram) temporally associated with the use of a medicinal product, whether or not considered related.

This requirement includes specific events or symptoms associated with cancer progression or general clinical deterioration to ensure potential toxicities are not overlooked. Radiographic progression without associated clinical sequelae is not considered an AE; terms such as 'disease progression' should be avoided. Pre-existing medical conditions that worsen during a study will be recorded as AEs. Abnormal laboratory values, ECG findings, or vital signs are to be recorded as AEs if they meet the criteria described in Section 9.3.

All untoward events that occur after informed consent through 30 days (100 days for SAEs and AESIs) after the date of the decision to permanently discontinue study treatment (defined as the later of the date of the decision to discontinue all study treatment or the date of the last dose of any study treatment) are to be recorded by the investigational site.

At each scheduled and unscheduled visit, AEs are to be identified and assessed based upon study procedures, routine and symptom-directed clinical investigations, and subject query/report.

Assessment of the relationship of the AEs to study treatment by the investigator will be based on the following two definitions:

- Not Related: An event is assessed as not related to study treatment if it is attributable to another cause and/or there is no evidence to support a causal relationship.
- Related: An event is assessed as related to study treatment when there is a reasonable possibility that study treatment caused the event. Reasonable possibility means there is evidence to suggest a causal

relationship between study treatment and the event. This event is called a suspected adverse reaction. A suspected adverse reaction implies a lesser degree of certainty about causality than adverse reaction, which means any AE caused by a drug.

9.2.1.2. *Severity of Events*

Assessment of adverse events, safety, and toxicity will be performed according to the National Cancer Institute Common Toxicity Criteria (version 5.0) from the time of Informed Consent for the pre-registration phase until the end of study. The following definitions should be considered when evaluating the severity of oncology events when not present in NCI-CTCAE version 5.0:

Severity of Events	
Grade	Definition
1	Mild adverse event
2	Moderate adverse event
3	Severe and undesirable adverse event
4	Life-threatening or disabling adverse event
5	Death related to adverse event

9.2.1.3. *Laboratory Abnormalities*

All laboratory data required by this protocol and any other clinical investigations will be reviewed. Any abnormal value that leads to a change in subject management (eg, dose reduction or delay or requirement for additional medication or monitoring) or that is considered to be of clinical significance by the Investigator will be reported as an AE or SAE as appropriate, unless this value is consistent with the subject's present disease state or is consistent with values obtained prior to entry into the study.

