Diarrhoea, nausea/vomiting, decreased appetite, and stomatitis/oral pain were some of the most commonly reported GI adverse reactions. Prompt medical management, including supportive care with antiemetics, antidiarrheals, or antacids, should be instituted to prevent dehydration, electrolyte imbalances and weight loss. Dose interruption or reduction, or permanent discontinuation of cabozantinib should be considered in case of persistent or recurrent significant GI adverse reactions.

Diarrhea occurred in 63% of patients treated with cabozantinib. Grade 3 diarrhea occurred in 11% of patients treated with cabozantinib.

Withhold cabozantinib until improvement to Grade 1 and resume cabozantinib at a reduced dose for intolerable Grade 2 diarrhea, Grade 3 diarrhea that cannot be managed with standard anti diarrhea treatments, or Grade 4 diarrhea.

5) Thrombotic Events

Cabozantinib increased the risk of thrombotic events. Venous thromboembolism occurred in 7% (including 4% pulmonary embolism) and arterial thromboembolism occurred in 2% of cabozantinib-treated patients. Fatal thrombotic events occurred in cabozantinib-treated patients.

Discontinue cabozantinib in patients who develop an acute myocardial infarction or serious arterial or venous thromboembolic events that require medical intervention

6) Hemorrhage

Severe and fatal hemorrhages occurred with cabozantinib. The incidence of Grade 3 to 5 hemorrhagic events was 5% in cabozantinib-treated patients. Discontinue cabozantinib for Grade 3 or 4 hemorrhage. Do not administer cabozantinib to patients who have a recent history of hemorrhage, including hemoptysis, hematemesis, or melena.

7) Thrombocytopenia

In the HCC study (CELESTIAL), thrombocytopenia and decreased platelets were reported. Platelet levels should be monitored during cabozantinib treatment and the dose modified according to the severity of the thrombocytopenia (see section 7.1.2).

8) Wound Complications

Wound complications have been reported with cabozantinib. Stop cabozantinib at least 28 days prior to scheduled surgery. Resume cabozantinib after surgery based on clinical judgment of adequate wound healing. Withhold cabozantinib in patients with dehiscence or wound healing complications requiring medical intervention.

9) Hypertension and Hypertensive Crisis

Cabozantinib can cause hypertension, including hypertensive crisis. Hypertension was reported in 36% (17% Grade 3 and <1% Grade 4) of cabozantinib treated patients.

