9.3. SERIOUS ADVERSE EVENT (SAE)

9.3.1. Definitions

The SAE definition and reporting requirements are in accordance with the ICH Guideline for Clinical Safety Data Management: Definitions and Standards for Expedited Reporting, Topic E2A.

An SAE is any AE occurring at any dose that:

- o Results in death.
- o Is immediately life-threatening (ie, in the opinion of the investigator, the AE places the subject at immediate risk of death; it does not include a reaction that, had it occurred in a more severe form, might have caused death).
- o Requires inpatient hospitalization or results in prolongation of an existing hospitalization.
- o Results in significant incapacity or substantial disruption of the ability to conduct normal life functions.
- o Is a congenital anomaly or birth defect.

- o Is an important medical event that may not be immediately life-threatening, result in death, or require hospitalization, but may be considered an SAE when, based upon appropriate medical judgment, it jeopardizes the subject or may require medical or surgical intervention to prevent one of the outcomes listed above.

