9.4. ADVERSE EVENTS OF SPECIAL INTEREST

Adverse events of special interest (AESIs) consist of immune-mediated AEs associated with ICIs, cases of potential DILI, and suspected transmission of an infectious agent by the study treatment (Table 3).

AESIs will be reported to the Sponsor or designee using the SAE reporting form irrespective of whether the event is serious or nonserious; all AESIs must be reported within 24 hours using the SAE process as described in Section 9.3.

Guidance for management of immune-mediated AEs associated is provided in Investigator's Brochure for atezolizumab.

Table 3. Adverse Events of Special Interest

Category	Event
DILI	
Cases of potential Drug-induced Liver Injury (DILI) that include an elevated ALT or AST in combination with either an elevated bilirubin or clinical jaundice, as defined by Hy's Law and based on the following observations:
Treatment-emergent ALT or AST $> 3 \times$ baseline value in combination with total bilirubin $> 2 \times$ ULN (of which $\geq 35\%$ is direct bilirubin).Treatment-emergent ALT or AST $> 3 \times$ baseline value in combination with clinical jaundice.
Other	
Suspected transmission of an infectious agent by the study treatment, as defined below:
Any organism, virus, or infectious particle (eg, prion protein transmitting transmissible spongiform encephalopathy), pathogenic or non-pathogenic, is considered an infectious agent. A transmission of an infectious agent may be suspected from clinical symptoms or laboratory findings that indicate an infection in a patient exposed to a medicinal product. This term applies only when a contamination of study treatment is suspected.
irAE	
Systemic lupus erythematosus
irAE	
Events suggestive of hypersensitivity, infusion-related reactions, cytokine release syndrome, HLH and MAS
irAE	
Nephritis
irAE	
Ocular toxicities (eg, uveitis, retinitis)
irAE	
\geq Grade 2 cardiac disorders (eg, atrial fibrillation, myocarditis, pericarditis)
irAE	
Vasculitis
irAE	
Autoimmune hemolytic anemia

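### Section 9.2.1.1 tests abnormal laboratory, ECG and vital-sign values against Section 9.3, which holds only seriousness criteria, so non-serious values, most clearly raised blood pressure, may be left out of the AE record

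*Combined protocol and SAP*

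**What the plan says.** Protocol Section 9.2.1.1 contains two statements on abnormal measurements. Its opening definition counts as an AE "the abnormal results of an investigation (e.g. laboratory findings, electrocardiogram) temporally associated with the use of a medicinal product", and any unfavourable sign, with no seriousness condition. Further down it gives a recording rule: "Abnormal laboratory values, ECG findings, or vital signs are to be recorded as AEs if they meet the criteria described in Section 9.3".

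Section 9.3 is the SAE section. Its list in 9.3.1 begins "An SAE is any AE occurring at any dose that" and consists of seriousness outcomes: death, immediate threat to life, hospitalisation, incapacity, birth defect, or an important medical event.

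Section 9.2.1.3, headed as dealing with laboratory abnormalities, sets another test: "Any abnormal value that leads to a change in subject management", or "that is considered to be of clinical significance by the Investigator will be reported as an AE or SAE as appropriate". It excepts values in line with the patient's current disease or with pre-study values.

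In Section 7.1.3 the protocol gives a rate for one toxicity found by measurement: "Hypertension was reported in 36% (17% Grade 3 and <1% Grade 4) of cabozantinib treated patients".

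**The concern.** The recording rule points to a list that contains no criterion for a non-serious value. Two thresholds that lie far apart, seriousness on one side and a management change or clinical significance on the other, both claim to decide when a measured abnormality becomes an AE. No passage says which prevails.

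At stake is the safety endpoint (protocol 10.2.2, SAP 1.2.2), which rests largely on counts of patients with AEs, by CTCAE grade. If some sites treat the 9.2.1.1 sentence as the operative threshold and others follow 9.2.1.3, the same blood-pressure reading could be an AE at one site and not at another. The any-grade and Grade 3 or higher tables would then depend partly on how each site read the protocol.

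**Working it through.** The plan states no figure to reproduce. The check compares passages and then sets a scale.

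**1. Does Section 9.3 mean the SAE section?** Yes. Section 9.4 uses the same number in that sense: "all AESIs must be reported within 24 hours using the SAE process as described in Section 9.3". The reference in 9.2.1.1 therefore does land on the seriousness criteria. It is probably a misdirected cross-reference, with 9.2.1.3 the likely target. Section 9.6.2 has a similar slip: it cites Sections 9.1 and 9.2 for AE and SAE reporting, although SAE reporting is in 9.3.2.

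**2. What other recording rule exists for each kind of value?**

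| Kind of value | Other explicit rule | Seriousness needed? |
|---|---|---|
| Laboratory | 9.2.1.3; also 9.4 for potential drug-induced liver injury | No |
| ECG | 8.2.1 and 8.2.3: clinically significant abnormalities go to medical history or AE | No |
| Vital signs | None of their own; 8.2.1 to 8.2.3 say only what to measure | Not stated |

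Vital signs can be reached indirectly. Section 9.2.1.3 opens by mentioning other clinical investigations besides laboratory data, and the general definition in 9.2.1.1 covers unfavourable signs, with tachycardia as an example. Neither is an explicit criterion for blood pressure.

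**3. Would the values still appear in the output?** Protocol 10.6 and 10.7 and SAP 1.5 promise graded laboratory values, and tables of vital signs, ECG and laboratory data with out-of-range values flagged. However, the SAP safety shells (2.6 and 2.7) are all built from AE or SAE records, and the laboratory, ECG and vital-sign shells shown (2.2) are baseline tables. The separate tabulation is promised in the text but has no on-treatment shell.

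**4. Scale, using hypertension.** Inputs: 36% any grade, 17% Grade 3 and under 1% Grade 4 (Section 7.1.3); 54 to 144 planned patients (synopsis). Assumption: these rates apply to this trial. Expected number = planned patients × rate.

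- Any grade: 54 × 0.36 = 19.4; 144 × 0.36 = 51.8.
- Grade 3: 54 × 0.17 = 9.2; 144 × 0.17 = 24.5.
- Grade 1 to 2: 36% − 17% − (0 to 1%) = 18 to 19%. This gives 54 × 0.18 = 9.7 to 54 × 0.19 = 10.3, and 144 × 0.18 = 25.9 to 144 × 0.19 = 27.4.

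The documents give neither the share of hypertension that would be serious nor how sites read the sentence. The number omitted therefore cannot be computed. Its bounds are zero and the counts above.

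**The case against.** The best defence is that the sentence says *if*, not *only if*. Read that way, it adds a route into the AE record and closes none, so it can stand beside 9.2.1.3. An exclusive reading is also circular, because 9.3.1 defines an SAE as an AE that is serious, so the value must already be an AE before 9.3 applies. Many non-serious values are captured elsewhere: by the general definition, by 9.2.1.3 (which includes values that lead to added medication or monitoring), by the ECG rule, by the rule in 8.2.1 to 8.2.3 on new clinically significant examination findings, and by the AESI rule in 9.4. Treated hypertension plausibly falls under 9.2.1.3, or counts as a new medical condition under 9.2.1.1.

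Much of this stands. It rules out the stronger inference that only serious values are AEs under this protocol, and the inference that reported AE rates are biased low. The documents show a risk of omission; they do not demonstrate a bias.

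It does not rescue the sentence. A statement that sets a criterion for recording is naturally read as a threshold, and as written the threshold is the wrong one. The broader definition in the same section adds to the inconsistency without telling a site which statement governs.

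**Conclusion.** Wrong as written, and minor. The cross-reference in 9.2.1.1 leads to seriousness criteria and conflicts with 9.2.1.3 and with the section's own AE definition. The exposure is clearest for vital signs, blood pressure above all; laboratory and ECG values are largely protected by other rules. If the quoted hypertension rates apply, about 19 of 54 to 52 of 144 patients would have hypertension, about 9 to 24 of them Grade 3, and the number missed lies between zero and these counts. ORR, the stage rules and the sample size are unaffected.

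Two further inferences are tempting and should not be drawn. A reader might equate serious with Grade 4 and conclude that at most 24 × 0.01 = 0.24 hypertension cases per 24-patient cohort would be recorded. Nothing in the documents supports that equation, and the important-medical-event criterion in 9.3.1 reaches beyond Grade 4. A reader might also suppose that the commonest expected toxicities are the ones affected. Section 7.1.3 gives diarrhoea at 63% and palmar-plantar erythrodysesthesia at 44%, both above hypertension, and neither is a laboratory, ECG or vital-sign value.

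**What to change.** In 9.2.1.1, replace the reference to Section 9.3 with Section 9.2.1.3. In 9.2.1.3, state that the rule applies to laboratory values, ECG findings and vital signs, and adjust its heading to match. Send sites a short clarification. In data management, query out-of-range laboratory and blood-pressure values already collected that have no matching AE, so that records entered under the present wording are brought into line.

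The cost is one corrected reference, one added sentence, a site memo and a data query. Vital signs and laboratory tests are already scheduled at treatment visits (Table 2, Section 8.1), so no new assessment is needed, and no treatment rule changes.
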